9.3.2 Overdose

Overdose refers to the administration of a quantity of a medicinal product given per administration or per day which is above the protocol defined dosage.

The term overdose must be documented on the adverse event form of the eCRF book. In addition, AEs originating from overdose must be documented on a separate line.

9.3.3 Medication Error

Medication error refers to any unintentional error in the dispensing or administration of a medicinal product while in the control of the (sub)investigator or subject. Broadly, medication errors fall into four categories: wrong medication, wrong dose (including strength, form, concentration, amount), wrong route of administration or wrong subject.

The medication error must be documented on the adverse event form of the eCRF book. In addition, AEs originating from a medication error must be documented on a separate line specifying the category of error (see definitions above).

9.3.4 Misuse

Misuse refers to situations where the medicinal product is intentionally and inappropriately used not in accordance with the protocol.

The term misuse must be documented on the adverse event form of the eCRF book. In addition AEs originating from misuse must be documented on a separate line.

9.3.5 Abuse

Abuse relates to the sporadic or persistent, intentional excessive use of an IP which is accompanied by harmful physical or psychological effects.

The term abuse must be documented on the adverse event form of the eCRF book. In addition, AEs originating from abuse must be documented on a separate line.

9.3.6 Aggravation of Condition

Any clinically significant aggravation/exacerbation/worsening of any medical condition(s), compared to baseline, must be reported as an AE.

9.3.7 Lack of Efficacy

Not applicable

9.3.8 Adverse Events of Special Interest

In the clinical trials investigating LEO 43204 gel for AK in subjects with sun-damaged skin, there is a special interest for adverse events regarding development of keratoacanthoma (KA) or squamous cell carcinoma (SCC). Moreover, KA can be difficult to distinguish clinically and histologically from SCC. Sun-damaged skin is also prone to development of KA as a response to local irritation and/or inflammation. The subjects in this trial are not expected to have sun-damaged skin due to younger age and are thus considered to have a very low risk of developing KA or SCC.

To ensure that all information relevant for surveillance is collected, SCCs and KAs in the treatment area are considered adverse events of special interest (AESI).

For SCCs and KAs in the treatment area, the relevant information will be collected in the eCRF. In addition, histology report should be faxed or emailed to Global Pharmacovigilance, once available, using the following fax number or email address:

[contact]

Email address: [contact]

SCCs and KAs in the treatment area that meet the criteria for being serious should be reported as SAEs (please refer to section 9.4.1 for reporting details).

The pathology slides that have been used for the initial diagnosis of SCC or KA will be sent for central pathology review. Central pathology reports will be distributed to the investigator. If there are any discrepancies between the local pathology report and the central pathology report, there should not be any changes in the eCRF. For the central pathology review, the local pathology laboratory will send the relevant histology slides to the investigator who will forward the slides to the pathologist doing the central reading. Only if the original slides cannot be sent is it acceptable to use new slides made from the tissue block.

9.4 Additional Reporting Requirements for Serious Adverse Events

9.4.1 Investigator Reporting Responsibilities

Any Serious Adverse Event (SAE) must be reported to LEO on the (paper) Serious Adverse Event Form – Clinical Trials within 24 hours of first knowledge. This report should contain an assessment of available information on seriousness, severity, causal relationship to the IP, comparator or trial procedure, the action taken, the outcome to date, and a narrative description of the course of the event.

Any LSR classified as a SAE must be added to the adverse event form in the eCRF and in addition reported to LEO on the SAE form.

The completed SAE form must be faxed or scanned and e-mailed to Global Pharmacovigilance, LEO using the following fax number or e-mail address:

[contact] (for Global Pharmacovigilance)

E-mail address: [contact] (for Global Pharmacovigilance)

It may be relevant for the (sub)investigator to enclose other information with the SAE form, such as reports of diagnostic procedures, hospital records, autopsy reports, etc.

Additionally, Global Pharmacovigilance, LEO may request further information in order to fully assess the SAE. The (sub)investigator must forward such information to Global Pharmacovigilance, LEO upon request by fax or e-mail (see contact details above).

The investigator must notify the local IRB(s)/IEC(s) of SAEs as required by current applicable legislation for the concerned country.

SAEs occurring after the completion of the clinical trial including any protocol required post-treatment follow-up period should not be routinely sought or collected. However, such events should be reported to Global Pharmacovigilance, LEO ([contact]) if the (sub)investigator becomes aware of them.

9.4.2 LEO Reporting Responsibilities

Global Pharmacovigilance, LEO is responsible for assessing whether or not a SAE is expected. The relevant reference document for this clinical trial is:

For the IP, the Investigator's Brochure, LEO 43204 gel, Field Therapy, Edition No. 4 including Addendum of LEO 43204 gel in Acne Vulgaris (Exploratory Edition No. 1) and subsequent updates hereof must be used.

Global Pharmacovigilance, LEO will notify the regulatory authorities and concerned investigators of SAEs according to the current applicable legislation for the concerned country.

The IRB(s)/IEC(s) will be notified of SAEs according to the current applicable legislation for the concerned country.

For the US, all SAEs which are assessed as causally related to the IP by LEO (Guidance for Industry and Investigators – Safety Reporting Requirements for INDs and BA/BE Studies) and which are unexpected (Serious and Unexpected Suspected Adverse Reactions (IND safety report)) are subject to expedited reporting to regulatory authorities and IRB(s)/IEC(s) according to current applicable legislation in the concerned country. Investigators will be notified of these on an ongoing basis.

9.5 Follow-up for Final Outcome of Adverse Events

During the trial, the investigator should follow up for final outcome on all AEs (including SAEs). Once a subject has completed the clinical trial, LSRs as well as AEs classified as possibly or probably related to the IP that are deemed clinically significant should be followed for 2 months or until final outcome is determined, whichever comes first.

SAEs must be followed up until a final outcome has been established, i.e. the follow-up may continue beyond the end of the clinical trial.

10 Investigational Product(s)

10.1 Investigational Product Description

Finished product (brand) name (if available)/name investigational product	LEO 43204, 0.018%
Formulation	Gel
Active ingredient name/concentration	LEO 43204, 0.018% w/w
Excipients	CCI [REDACTED]
Pack size(s)	1 g laminate tubes each containing 0.67g
Manufacturer's name of bulk medication (IP)	LEO Pharma [name] Or LEO Laboratories LTD. [name]
Certifier's name of bulk medication (IP)	LEO Pharma A/S
Supplier's name	LEO Pharma A/S,
Manufacturer's name of subject treatment packages	CCI [REDACTED]
Certifier's name of subject treatment packages	LEO Pharma A/S
Finished product (brand) name (if available)/name investigational product	Vehicle gel
Formulation	Gel
Active ingredient name/concentration	Not applicable
Excipients	CCI [REDACTED]
Pack size(s)	1 g laminate tubes each containing 0.67g

Manufacturer's name of bulk medication (IP)	LEO Pharma [name] Or LEO Laboratories LTD. [name]
Certifier's name of bulk medication (IP)	LEO Pharma A/S
Supplier's name	LEO Pharma A/S,
Manufacturer's name of subject treatment packages	CCI [REDACTED]
Certifier's name of subject treatment packages	LEO Pharma A/S

10.2 Administration of Investigational Products

Route of administration	Topical administration
Application range	Left and right cheek treatment areas (TA _{left} and TA _{right}) corresponding to approximately 36 cm ² each.
Application frequency	Once daily for up to three consecutive days
Daily maximum	Approximately 1/3 of a tube per TA applied by the trial staff as a thin wet layer.
Time of day for application	No specific requirements
Relation of time of application to dietary intake	No specific requirements

The IP will be applied to the treatment areas at the clinic by the trial site staff .

10.2.1 Trial Medication Application

At each application, a thin wet layer of trial medication should be applied evenly within the identified TA of approximately 36 cm² by the trial site staff. The required total amount of IP to produce a thin wet layer is approximately 1/3 of a squeezed tube and equal to a pea-sized drop. The trial staff will be trained to dispense the correct amount of IP. Prior to application, the location of the TA is identified using a transparent film and a three-point landmark technique ([Appendix 10](#)).

Trial medication should be applied according to the following procedure:

1. Using standard hospital gloves, remove the cap from the unit dose tube. Squeeze a pea-sized drop of IP from tube onto the index finger.

2. Spread the trial medication evenly over the assigned treatment areas such that a thin wet layer of IP is applied.
3. Recap the tube and store for drug account (refer to section 10.7).
4. Dispose of gloves and wash hands with soap and water.
5. Allow the trial medication to dry for at least 15 minutes following application.

General treatment guidance:

- Subjects should not shave or trim the treatment areas during the treatment days.
- Subjects should not wash the treatment areas on the treatment days prior to IP application.
- Subjects must avoid washing the treatment areas or engaging in activities that cause excessive sweating for at least 6 hours following IP application.
- When subjects resume their normal washing routine, they should wash the treatment areas gently using a mild soap.
- Subjects should avoid use of non-medicated/non-irritant salves/emollients on the treatment areas during treatment days and within 3 days prior to the first treatment day.
- Subjects should avoid use of make-up and sunscreens on the treatment areas from 3 days prior to first treatment day and 15 days after last IP application. Note: Eye-make-up within peri-orbital area and lipstick is allowed.
- Subjects should be advised not to allow other persons (including children) and pets to come into contact with the treatment areas for a period of 6 hours following application.
- Subjects should avoid contact of IP with eyes.
- Subjects should avoid excessive sun exposure (e.g. sunbathing, tanning booths) of the treated area.

10.3 Precautions/Over dosage

10.3.1 Skin exposure

The most common LSRs reported in the AK studies with LEO 43204 gel are erythema, flaking/scaling, and crusting. Less common LSRs include swelling/oedema, vesiculation/pustulation, and erosion/ ulceration. Completed clinical trials have shown LSRs to be transient and normally resolved within two weeks (please refer to the Investigator's Brochure of LEO 43204 gel in Actinic Keratosis Edition 4 or any updates hereof for further details).

In a low percentage of subjects treated on face or scalp, swelling around the eyes or on the eyelids may develop to a point where it may be considered clinically significant. In such cases these AEs should be recorded as peri-orbital oedema or eyelid edema. Treatment is usually straightforward with cold compress on the eye(s) with the subject resting in supine position for a few hours.

The mean maximum composite LSR score in Part 2 of LP0084-1013 (face) for the doses of LEO 43204 gel that will be used in the current trial was 8.9 for face. Using the same doses for 3 consecutive days (LP0084-1148), mean maximum composite scores were 10.6 for face. Peak value in the LP0084-1013 trial (face) was at Day 3. At Day 15, mean maximum composite LSR score was either at baseline value or close to baseline value in almost all subjects treated on face (refer to the Investigator's Brochure of 43204 gel in Actinic Keratosis Edition 4 or any updates hereof).

Investigators conducting clinical trials with LEO 43204 gel should ensure that investigational site staff is trained in the protocol-specified application procedure(s) and follow appropriate precautions. Investigators must monitor their subjects for the emergence and resolution of LSRs and AEs

10.3.2 Ocular Exposure

If accidental eye exposure occurs, the eye should be irrigated immediately and extensively with water. The subject should immediately seek medical attention by contacting the investigator or other medically qualified healthcare professional (e.g., in an Emergency Room) for assessment and treatment. All treatments are to be administered at the discretion of the healthcare professional (in emergency room, ophthalmologist, and/or the investigator). Treatment with topical cycloplegic and topical ophthalmic antibiotics is recommended. Topical anti-inflammatory agents and eye pads may also be useful for subject comfort. The subject should be monitored closely in the first few days following exposure to check for secondary infection and to assess visual acuity. Subjects should be warned that vision might worsen before improvement occurs.

Any suspected ocular exposure should be documented and brought to the attention of the monitor

10.3.3 Other Exposure

LEO 43204 gel must not be ingested. If accidental ingestion occurs the subject should drink plenty of water.

10.4 Packaging of Investigational Products

The IP will be packaged in individually numbered kits. Each kit contains 2 unit-dose tubes.

Each unit-dose tube will contain LEO 43204 gel or vehicle gel to be handled in the hospital clinic up to three consecutive days.

The label on the tubes will be colored (e.g. red and green) to instruct the site personnel on which site (left or right) the product should be applied.

The labeling of trial products must be in accordance with Annex 13, local regulations and trial requirements.

10.5 Storage of Investigational Products

All LEO supplied drugs must be stored in a secure and restricted area under the conditions specified on the label and remain in the original container until dispensed.

The IP must be stored in a refrigerator between 2°C and 8°C (36°F to 46°F). The refrigerator temperature must be monitored continuously and recorded. Do not freeze.

10.6 Treatment Assignment

Subjects who have been found to comply with all the inclusion criteria and not to violate any of the exclusion criteria will be randomised to receive treatment with LEO 43204 gel and vehicle gel to the treatment areas identified on three consecutive days.

10.6.1 Randomisation Code List

The randomisation files must be kept during the clinical trial in a secure area on the database server at LEO inaccessible to staff involved with the conduct and administration of the clinical trial until the clinical trial is unblinded.

10.7 Drug Accountability and Compliance Checks

10.7.1 Drug Accountability

The investigator is fully responsible for the investigational products at the trial site and for maintaining adequate control of the investigational products and for documenting all transactions with them.

An inventory must be kept of the investigational product given to each subject randomised in the trial. This inventory must be available for inspection during monitoring visits and will be checked by the monitor to ensure correct dispensing of the investigational product.

All investigational products supplied by the Contract Manufacturing Organisation (CMO) on behalf of LEO must be returned to the CMO. Prior to their return, they must be fully accounted for by the monitor with the help of the person responsible for dispensing the investigational products. Accountability must be documented by using drug accountability forms.

Investigational products may be returned from the trial site directly to the CMO responsible for the running of the clinical trial.

10.7.2 Trial Product Destruction

Used and unused trial products will be destroyed by the CMO according to LEO procedures.

10.7.3 Treatment Compliance

Treatment is performed at the clinic according to the protocol by the trial site staff.

10.8 Emergency Unblinding of Individual Subject Treatment

While the safety of a subject always comes first, it is still important to seriously consider if unblinding is necessary to ensure subject's safety. This section describes the procedures for unblinding a subject. An emergency unblinding request can be made by the (sub)investigators, other health care professionals or authorized LEO personnel.

Provisions are in place for 24 hour emergency unblinding of individual subject treatment. If emergency unblinding is required, the individual subject's treatment assignment can be obtained via the IWRS. Requester without access to IWRS (Health Care Professionals), can contact the investigator or LEO for emergency unblinding.

11 Statistical Methods

11.1 Determination of Sample Size

With a sample size of 38 subjects the power of observing a difference between active and vehicle gel will be 84% in a trial with intraindividual comparisons, using a paired two-sided t-test on a 5% level, assuming an approximate total lesion count of 36 at baseline and reductions at end of trial from baseline around 7.3 (20%) and 12.4 (34%) for vehicle gel and active respectively, and a standard deviation of the difference between treatments at end of treatment up to 10.4.

The assumptions on sample size are that all but the two first subjects of the 40 subjects randomised are included in the efficacy analyses, and the assumptions on efficacy rely on experiences from a previous trial conducted by LEO in subjects suffering from acne vulgaris

(LP0045-01), together with an expected reduction in standard deviation of the primary endpoint of at least 20% due to the intraindividual comparisons.

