6.2 Sample Size

A total of 40 subjects (male and female) will be randomised. Subjects withdrawn after randomization will not be replaced.

The expected statistical properties of the primary endpoint are described in section [11.3.4](#).

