7.7 Withdrawal Criteria

Subjects **may** withdraw from the trial for any of the following reasons:

1. Unacceptable treatment efficacy: the (sub)investigator is free to withdraw the subject at any time based on a medical judgment.
2. Unacceptable AEs or LSRs: any AEs or LRS that the (sub)investigator or the subject considers unacceptable.
3. Exclusion criteria: any exclusion criteria which emerge/become apparent during the subject's participation in the clinical trial.
4. Voluntary withdrawal: subjects are free to withdraw from the clinical trial at any time and for any reason.
5. Subjects must withdraw from the trial for any of the following reasons:
 - a. Subject becomes pregnant during the trial.
 - b. Subject with positive pregnancy test at screening and/or Day 1 will be excluded and complete End of Trial Form. Subjects with positive pregnancy test at visits after treatment (Week 2, 4, 8, or 12) may remain in trial for follow up.

Reason(s) for withdrawal must be recorded in the eCRF and medical records.

Subjects who are discovered, after enrolment/randomisation, not to have fulfilled all in-/exclusion criteria at the time of enrolment should discontinue treatment unless the (sub)investigator, based on clinical and ethical evaluation, finds discontinuation inappropriate.

Subjects who discontinue treatment after at least one treatment should remain in the trial for follow-up assessments. AEs should be followed up in all subjects as described in section 9.5

Subjects withdrawn will not be substituted.

8 Trial Schedule and Assessments

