11.2 Definition of Trial Analysis Sets

All subjects enrolled in the trial (i.e. subjects for whom informed consent has been obtained and who have been registered in the clinical trial) will be accounted for in the clinical trial report.

All subjects randomised except the first two subjects with a reduced exposure are included in the full analysis set and will be analysed for efficacy. The size of the full analysis set will then be 38 subjects. Exclusions from the full analysis set can be considered in special cases as described in ICH E9, section 5.2.1. Full Analysis Set. If it is decided to exclude a randomised subject from the full analysis set, a justification addressing ICH E9 will be given.

A per protocol analysis set will be defined by excluding subjects from the full analysis set based on the review of protocol deviations before the unblinding of the trial. If it is decided to exclude a subject from the per protocol analysis set, a justification will be given.

A safety analysis set will be defined by excluding subjects from the full analysis set who either received no treatment with investigational product and/or for whom no post-baseline safety evaluations are available.

The decisions regarding inclusion/exclusion of subjects and/or subject data from the trial analysis sets will be documented in the statistical analysis plan update before breaking the randomisation code.

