Appendix 10: Identifying and Documenting the Treatment Area

Appendix 11: Acne QoL

Appendix 12: TSQM II

25 Appendix 1: Protocol Summary

Name of finished/ investigational product	LEO 43204 gel 0.018%
Name of active substance	LEO 43204
Title of trial/trial ID/	Explorative trial evaluating the efficacy, tolerability and safety of LEO 43204 applied in a split-face (left/right) topical design in adults with moderate to severe acne / EXP-1223
International Coordinating Investigator	[name].
Sponsor's name/ address	LEO Pharma A/S, [name]
Estimated number of trial sites and distribution	Single site in USA
Trial period	Planned date of enrolment of first subject: Q2-2016 Planned date of completion of last subject: Q4-2016
Main objective(s)	To assess the efficacy of treatment with LEO 43204 gel and vehicle gel on acne vulgaris disease severity 12 weeks after end of treatment. Treatment is defined as once daily application of LEO 43204 gel and vehicle gel for up to 3 days
Methodology	Phase 2a, Single centre, prospective, randomised, vehicle-controlled, double-blinded, split-face (left/right) design trial
Number of subjects to be enrolled	Planned to enroll 40 subjects Planned to complete 30 subjects
Main criteria for inclusion	
 • Subjects should be diagnosed with moderate to severe acne vulgaris of the face. • Fitzpatrick skin types I-III (due to lack of safety data for the investigational product in darker skin types) • Lesions should be relatively symmetrical in appearance on both sides of the face (asymmetrical disposition of acne lesions defined as: the number of acne lesions on any hemiface is greater than twice the number on the other hemiface for either inflammatory or non-inflammatory lesions). • Male or female aged 18 to 35 years inclusive.

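### The 84% power rests on 38 subjects, but Appendix 1 plans for 30 of 40 to complete; if that means Week 12 data, complete-pair power is about 74% at the stated SD limit

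*Protocol*

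**What the plan says.** Protocol section 11.1 gives the power statement: "With a sample size of 38 subjects the power of observing a difference between active and vehicle gel will be 84" per cent. It assumes a paired two-sided t-test at the 5% level, a baseline total count of about 36, reductions of about 7.3 (vehicle) and 12.4 (active), and "a standard deviation of the difference between treatments at end of treatment up to 10.4". The 38 comes from the assumption that "all but the two first subjects of the 40 subjects randomised are included in the efficacy analyses". Section 11.2 repeats it: "The size of the full analysis set will then be 38 subjects".

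Appendix 1 (Protocol Summary) plans to enrol 40 subjects and then says "Planned to complete 30 subjects". It does not say what a subject must do to count as complete, or whether the first two subjects are included.

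Withdrawals shrink the sample for good. Section 6.2 says "Subjects withdrawn after randomization will not be replaced", and section 7.7 says "Subjects withdrawn will not be substituted". Section 7.7 also separates stopping treatment from leaving the trial: "Subjects who discontinue treatment after at least one treatment should remain in the trial for follow-up assessments".

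Missing Week 12 counts are multiply imputed for the primary analysis on the full analysis set, separately by lesion type and treatment group. Last observation carried forward and observed cases are sensitivity analyses (protocol section 11.3.12, SAP section 4.3.1).

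**The concern.** The power calculation treats 38 subjects as 38 observed active-minus-vehicle differences at Week 12. The same protocol appears to expect 10 of 40 subjects (25%) not to complete, with no replacement. Section 11.1 does not mention the 30, and no passage connects it to the 38.

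At stake is how a non-significant result is read. Section 11.1 implies about a 16% chance of missing the assumed 5.1-lesion difference. If only 30 subjects, or 28 of those in the efficacy set, were expected to have Week 12 counts, the planned risk on complete pairs was appreciably higher. Section 3.4 also justifies the within-subject design partly by the power it gives with few exposed subjects, so the power figure supports more than the statistics section.

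**Working it through.** **Inputs, all from protocol section 11.1 unless noted**
- Difference between treatments: 12.4 − 7.3 = 5.1 lesions
- SD of the within-subject difference: 10.4, stated as an upper limit
- Paired t-test, two-sided, alpha 0.05
- Pairs: 38 (sections 11.1 and 11.2), or 30 (Appendix 1). If the 30 include the two subjects left out of efficacy, 30 − 2 = 28.

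**Formula.** Power comes from the noncentral t distribution with n − 1 degrees of freedom and noncentrality (5.1/10.4) × √n = 0.490 × √n, at the two-sided 5% critical value.

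**The plan's own figure.** For n = 38 the noncentrality is 0.490 × 6.164 = 3.02 and the power is 83.7%, which rounds to the stated 84%. There is no arithmetic error in section 11.1.

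**Same inputs, fewer complete pairs.** The last column is the half-width of the 95% confidence interval for the difference, t(0.975, n − 1) × 10.4/√n.

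| Complete pairs | Power | Chance of missing 5.1 lesions | 95% CI half-width (lesions) |
|---|---|---|---|
| 38 | 83.7% | 16% | 3.4 |
| 35 | 80.5% | 20% | – |
| 34 | 79.3% | 21% | – |
| 30 | 73.8% | 26% | 3.9 |
| 28 | 70.6% | 29% | 4.0 |

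The smallest number of pairs with at least 80% power is 35. At an SD of 10.4, no more than 38 − 35 = 3 subjects of the full analysis set can lack a Week 12 pair before complete-pair power drops below 80%.

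**Dependence on the SD.** Because 10.4 is an upper limit, the calculation was also solved for the SD that restores 84%. It is 9.14 with 30 pairs and 8.80 with 28. For 80% the values are 9.64 and 9.29.

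Section 11.1 expects the within-subject comparison to reduce the SD by at least 20%. If 10.4 reflects exactly 20% (an assumption; the documents do not say), the unreduced SD would be 10.4/0.8 = 13.0. An SD of 9.14 would then need a reduction of 1 − 9.14/13.0 = 30%. The documents neither support nor exclude that.

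**The case against.** The strongest reply is that 38 and 30 measure different things. The 38 is the size of the full analysis set and the 30 is a number of completers. With imputation of Week 12 counts, a set of 38 can coexist with 30 completers. This stands as far as it goes: the set size is not contradicted. But the power statement is for a paired t-test on 38 pairs, and imputation does not supply the missing observations.

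Related to this, 74% is not the power of the planned primary analysis. That is an ANCOVA with baseline count as covariate and subject as random effect, on imputed data. Baseline adjustment may change the residual variance, and earlier visits may recover some information. This also stands. The documents allow no figure for that analysis, and its power could lie on either side of the complete-pair figure. It cannot be assumed to return to 84%. The complete-pair figure bears most directly on the planned observed-cases sensitivity analysis.

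Two further points concern the 30 itself. Completing may mean completing treatment: Days 2 and 3 are conditional, and subjects not treated stay in follow-up, so on that reading no Week 12 data need be lost. The 30 may also be out of date. Appendix 1 differs from the body elsewhere: its symmetry criterion applies to inflammatory or non-inflammatory lesions per half-face, while section 7.2 uses the total count in the treatment areas. Its model also lists a site effect that section 11.3.4.1 lacks, although site may mean side of the face there. Both readings are open. They limit the claim about lost power, but they do not remove the unexplained mismatch.

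**Conclusion.** The concern holds as a matter of consistency. The 84% is correctly calculated for 38 complete pairs. It makes no allowance for missing Week 12 data, while Appendix 1 plans for 30 of 40 to complete and there is no replacement.

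The loss of power is conditional. It requires that completing means having Week 12 counts, that only complete pairs are analysed, and that the SD is at its 10.4 limit. Under those conditions power falls by about 10 percentage points with 30 pairs (83.7 − 73.8 = 9.9) and about 13 with 28 (83.7 − 70.6 = 13.1). Both results are below 80%. A smaller SD would offset this, and if the 30 refers to finishing treatment or is simply obsolete, the 84% need not change.

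The mismatch and the arithmetic are certain; which meaning of 30 applies is not. The point should be corrected, but it does not undermine the design or the analysis.

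**What to change.** First settle what the 30 means, then make one of two small changes.

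- If 30 is the number expected to have Week 12 counts, restate section 11.1 along these lines: *Power is 84% if all 38 subjects provide Week 12 data, and about 74% on complete pairs if 30 of them do, with an SD of the difference of 10.4.* If the 30 include the first two subjects, the second part should give about 71% with 28.
- If 30 is not that number, correct it in Appendix 1.

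In either case, Appendix 1 should say whether completing means attending Week 12 and whether the first two subjects are counted. The conditional sentence for section 11.1 is true whatever the 30 turns out to mean, so it can be added safely even if the origin of the figure cannot be traced.

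The cost is one sentence, or one figure with its definition. The only downside is a less favourable stated power. Enrolment and the planned analyses stay as they are.
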